## 9.0 PATIENT AND SUBJECT STATUS

#### 9.1 Pre-Screen Failure

During the Pre-Screening Process, if the PI and/or the Sponsor determine that the patient is not eligible for the study, the patient will be considered a Pre-Screen Failure. Pre-Screen Failures will be treated and followed according to standard of care by their Screening Dentist or endodontist, but will not be documented or followed for study purposes.

## 9.2 Pre-Screen Closure

If a patient is eligible and approved for the screening process, but does not complete a Baseline Visit, the patient will be considered a Pre-Screen Closure. Patients that fall into this category may have been lost or missed a scheduled Baseline Visit. In order for a patient to be considered lost, the clinical site should attempt contact with the patient at least three times. The first two attempts may be by phone call and must be documented. The third attempt must be made via certified letter.

## 9.3 Screen Failure

Patients who were consented but did not meet all Pre-Procedure and Intra-Procedure Inclusion Criteria and/or met any Pre-Procedure or Intra-Procedure Exclusion Criteria are considered Screen Failures. Screen Failures will be documented as such for the study but will be followed according to standard of care. Screen Failures will not be followed for the study.

## 9.4 Subject versus Patient

Once a patient is enrolled in the study, they are considered a subject.

## 9.5 Enrolled

Eligible patients will be considered enrolled after all Pre-and Intra-Procedure Inclusion Criteria are met and none of the Pre- and Intra-Procedure Exclusion Criteria are met.

## 9.6 Treatment Complete and Treatment Incomplete

Treatment Complete is defined by any subject that received 100% of the Sonendo GentleWave Treatment (Treatment).

Subjects that do not meet the Treatment Complete definition above are considered Treatment Incomplete.

## 9.7 Termination

Subjects may be terminated from the study at the discretion of the PI for reasons related to the study treatment that would jeopardize a subject's health and/or welfare if they were to continue in the study. Terminated subjects may be replaced. Terminated subjects may not be included in final data analysis. Notification of a subject termination should be made immediately to the Sponsor.

# 9.8 Withdrawal

Subjects may be withdrawn from the study for non-treatment-related reasons only when no other option is possible. Reasons for withdrawal include, but are not necessarily limited to, voluntary withdrawal from the study by the subject.

The reason for withdrawal will be recorded on the appropriate Case Report Form. Withdrawn subjects may be replaced in the study. Notification of a subject withdrawal should be made immediately to the Sponsor.

## 9.9 Discontinuation

Subjects may be discontinued from the study for non-treatment-related reasons only when no other option is possible. Reasons for discontinuation include, but are not necessarily limited to, a subject that is unwilling or unable to cooperate with study requirements (medication regimen, follow-up visits, etc.). The reason for discontinuation will be recorded on the appropriate Case Report Form. Discontinued subjects may be replaced in the study. Notification of a subject discontinuation should be made immediately to the Sponsor.

## 9.10 Lost to Follow-up

A subject that is consented but does not attend the study required visits and/or does not respond to contact attempts will be considered lost to follow-up. The clinical site should attempt contact with the subject at least three times. The first two attempts may be by phone call and must be documented. The third attempt must be made via certified letter.

If the subject is unable or unwilling to come in for a study visit, the process for mail, telephone call or general dentist contact should be attempted and documented (*see Section 7.19 Mail, Telephone and Dentist Contact*). Lost to follow-up subjects may be replaced in the study.

## **10.0 ADVERSE EVENTS**

## **10.1** Definition of Adverse Events

An adverse event (AE) is defined as any untoward medical occurrence in a subject. An AE can therefore be any unfavorable and unintended sign or symptom, intercurrent illness, injury, or disease temporally associated with treatment whether or not related to the procedure or device.

- Mild: The AE is transient and easily tolerated by the subject.
- Moderate: The AE causes the subject discomfort and interrupts the subject's usual activities.
- Severe: The AE causes considerable interference with the subject's usual activities, may be incapacitating and may require hospitalization.

## **10.2** Definition of Serious Adverse Events (SAE)

A serious adverse event (SAE) is defined as an adverse event that results in any of the following outcomes:

- Results in death
- Is life-threatening (defined as any AE that places a person, in the view of the Investigator, at immediate risk of death from the reaction as it occurred, i.e., it does not include an AE that, had it occurred in a more severe form, might have caused death)
- Requires in-patient hospitalization or prolongation of existing hospitalization
- Results in persistent or significant disability/incapacity (defined as a substantial disruption of a person's ability to conduct normal life functions)
- Is a congenital anomaly or birth defect.

## **10.3** Adverse Event Assessments

Adverse Events (AEs) that occur during the Baseline, Treatment Visit(s) and all the other Followup Visits including the Unscheduled Visits will be assessed by PI, recorded in the patient's study chart and then transcribed onto the Adverse Event Form Case Report Form (CRF).

Pain, inflammation, swelling, or other reactions that are expected and associated with standard traditional root canal or dental procedures will not be considered adverse events for the study.

Those events that may be exacerbated intra-procedure or post-procedure will be considered adverse events if the PI determines that these expected reactions are exacerbated or different from those experienced with the standard traditional root canal or dental procedures.

AEs include, but are not limited to, the following:

- Observed or volunteered problems
- Complaints
- Physical signs and symptoms
- Medical condition which occurs during the study, having been absent at baseline
- Medical condition present at baseline, which appears to worsen during the study.

AEs related to only dental and endodontic procedures will be collected for the study.

In addition to recording the AE on the Adverse Event CRF, the PI should also prepare an AE narrative (a complete written summary of the event and its outcome). Each AE must be described as follows:

• Describe the event by stating the underlying cause (the diagnosis), coexisting disease, or other. In order to avoid vague, ambiguous or colloquial expressions, the AE should be recorded in standard medical terminology rather than the subject's own words when

possible

- Note the duration by entering the date of onset, and date of resolution. If the event is present at the final study visit, the ongoing box must be marked
- Note the worst severity of the event as mild, moderate, or severe using the definitions provided in the protocol
- Note the outcome of the event
- Note the action taken as none, medical and/or surgical
- Note the relationship to surgical procedure and device
- Note any seriousness criteria

Any medication necessary for the treatment of an AE must be recorded on the Concomitant Medication CRF. If more than one distinct adverse event occurs, each event should be recorded separately.

In addition, PIs must report all AEs to their Institutional Review Board (IRB) and regulatory bodies according to applicable guidelines and regulations. A copy of the notification must also be submitted to the Sponsor.

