## **10.5** Assessment of Causality

Due to the temporal proximity of an AE to the procedure under investigation, there is a reasonable possibility that the procedure may have caused an AE or may have contributed to the severity or duration of an event caused by other means. Causality to the study procedure or device will be assessed by the PI and relationship will be classified in one of the following categories:

Definitely Not Related	Evidence exists that the adverse event definitely has a cause other than the procedure/device under investigation (e.g. pre-existing condition or underlying disease, intercurrent illness, or concomitant medication) and does not meet any other criteria listed.
Probably Not Related	An adverse event has little or no temporal relationship to the study device/study procedure and/or a more likely alternative etiology exists.
Possibly Related	A temporal relationship exists between the event onset and procedure under investigation, and appears with some degree of certainty to be related based on known therapeutic actions of the procedure/device under investigation. It cannot be readily explained by the patient's clinical state or concomitant therapies.
Probably Related	A temporal relationship exists between the event onset and procedure under investigation, and appears with some degree of certainty to be

- under investigation, and appears with some degree of certainty to be related based on known therapeutic actions of the procedure/device under investigation. It cannot be readily explained by the patient's clinical state or concomitant therapies.
- Definitely Related Strong evidence exists that the procedure/device under investigation caused the adverse event. There is a temporal relationship between the event onset and the procedure under investigation. There is strong therapeutic evidence that the event was caused by the procedure/device under investigation. The patient's clinical state and concomitant therapies have been ruled out as a cause.

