# **10.8** Anticipated Adverse Events

10.8.1 Risks generally associated with any dental procedure include, but are not limited to, the following:

• Pain and/or discomfort

Numbness

- Swelling or inflammation
- Pressure

- Paresthesia (tingling)
- Post-treatment infection

- Abscessed tooth
- Bleeding
- Tooth color changes
- Potential for re-treatment
- Reoccurring decay
- Reaction to medications or anesthesia
- Reaction to materials or chemicals used
- Sensitivity to hot and/or cold air

10.8.2 Potential risks for root canal therapy include, but are not limited to, the following:

- Post-treatment pain and/or discomfort
- Post-treatment swelling or inflammation
- Pressure
- Numbness
- Paresthesia (tingling)
- Post-treatment infection
- Abscessed tooth
- Bleeding
- Tooth color changes
- Potential for re-treatment
- Reoccurring decay
- Reaction to medications or anesthesia
- Reaction to materials or chemicals used
- Extrusion of debris into the periapical tissue

pressure or sweets

- Breakdown of the inner filling causing infection and/or damage
- Weakening of the tooth
- Instrument breakage within the canal
- Perforating (creating a small hole) the side of the root
- Tissue damage
- Tooth crown fracture or breakage
- Sensitivity to hot and/or cold, air pressure or sweets
- Breakdown of the inner filling causing infection and/or damage
- Defective or inadequate restoration of the tooth which could lead to infection, leakage, loosening, detachment, or breakage
- Uninstrumented recesses of the tooth (i.e. missed canals or uncleaned areas)
- Instrument separation (i.e. breakage within the canal)
- Perforating (creating a small hole) the side of the root
- Damage to sinus floor or sinus infection
- Tissue damage
- Root weakening
- Ledge formation

- Weakening of the tooth
- Jaw bone infection or damage
- Worn out filling

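### Section 10.3 collects only AEs related to dental and endodontic procedures and declassifies expected reactions, which conflicts with 10.1 and 10.6 and lets investigator attribution decide whether an event is recorded as an AE

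*Combined protocol and SAP*

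**What the plan says.** Section 10.1 gives a broad definition that takes in any "disease temporally associated with treatment whether or not related to the procedure or device".

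Section 10.3 then narrows it in two ways. On scope, "AEs related to only dental and endodontic procedures will be collected for the study". On expectedness, "Pain, inflammation, swelling, or other reactions that are expected and associated with standard traditional root canal or dental procedures will not be considered adverse events"; these events "will be considered adverse events if the PI determines that these expected reactions are exacerbated or different" from those seen with standard treatment. No threshold is given for that judgement. The same section also lists as AEs any medical condition that is new since baseline or has worsened since then. It puts the investigator's assessment ahead of entry in the chart and on the AE form.

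Section 10.5 has the investigator grade each AE on five levels. The lowest, Definitely Not Related, applies where "Evidence exists that the adverse event definitely has a cause other than the procedure/device under investigation". Section 10.6 requires all SAEs to be reported, and followed whatever the investigator thinks of the relationship.

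The primary safety endpoint (3.2) is the incidence of five named events, as related to the device: perforation, instrument separation, root fracture, sodium hypochlorite accident and Gutta Percha extrusion. Section 10.8 lists anticipated risks of root canal therapy, among them instrument separation and "Perforating (creating a small hole) the side of the root".

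**The concern.** The usual order is to record an event and then grade its cause, so that someone else can revisit the grade. Section 10.3 allows the reverse: a view on cause, or on whether a reaction is ordinary for root canal therapy, can settle whether an AE form exists. An event kept and graded unrelated can be re-assessed later. One never entered as an AE does not reach the AE tables.

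The study has one arm and a literature control (section 4.0). There is no concurrent group against which to judge whether a reaction is exacerbated or different, and sites may draw that line in different places. What is at stake is the completeness and between-site consistency of the AE data, and possibly of the primary safety endpoint.

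**Working it through.** The plan gives no AE rate and no share of unrelated or expected events, so there is no figure to reproduce. The check is a comparison of the sections.

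1. **10.1 against 10.3, scope.** 10.1 makes relatedness irrelevant to whether something is an AE. 10.3 makes a relationship to dental and endodontic procedures a condition of collection. An intercurrent illness is an AE under 10.1 and is not collected under 10.3. The conflict is direct.

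2. **10.3 against itself.** Its own list includes any new or worsened medical condition. Its scope sentence then excludes those that are not related to dental or endodontic procedures. It also asks for the relationship to procedure and device to be noted for each AE, which presupposes that the event was recorded before its relationship was settled.

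3. **10.6 against 10.3.** 10.6 covers all SAEs, and the scope sentence in 10.3 makes no exception for them. A serious event unrelated to dental procedures is required by one section and outside the other. This conflict is also direct.

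4. **10.5 against 10.3.** The 10.5 text for Definitely Not Related gives pre-existing and intercurrent conditions as examples, and most of those would not pass the 10.3 filter. The two tests are not identical, however. 10.3 refers to dental and endodontic procedures in general, 10.5 to the procedure or device under investigation. An event caused by other dental work passes 10.3 and can still be graded unrelated. The not-related grades are therefore narrowed, not emptied.

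5. **The expected exemption and the five primary safety events.** All five are dental, so the scope sentence should not remove them. The exemption is the weaker point. Perforation and instrument separation are on the 10.8 list of anticipated risks. 10.10 defines hypochlorite accident and extrusion of filling materials partly by pain, and the former also by swelling; these are signs that 10.3 exempts when expected. No sentence says that the five events are AEs regardless of expectedness.

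6. **What else captures events, by time (section 8.0 and sections 7.14 to 7.18).**
   - Pain: McGill at days 1, 2, 3, 7 and 14 and at every follow-up; Gracely DDS immediately after the procedure and at day 1. Both are outside the AE route.
   - Swelling, soft tissue lesions, percussion, palpation and periradicular diagnosis: at baseline and at 6, 12, 18 and 24 months, also outside the AE route.
   - Scheduled AE assessment: at the procedure and post-operatively, then not again until month 6.
   - Unscheduled visits: held only when an AE is suspected (7.18).

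   From the end of the procedure day to month 6, therefore, a non-pain event such as swelling, paresthesia, infection or abscess reaches the data mainly through the AE route, which 10.3 narrows.

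7. **Who applies the filter.** 10.3 does not say who decides that an event is related. That it is the investigator follows from 10.3, where the investigator assesses events and lifts the exemption, and from 10.5, where the investigator grades causality.

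**The case against.** The strongest reply is that much reaches the sponsor regardless of AE status. Investigator-signed, redacted source documents go to the sponsor after each study visit (7.4.4, 7.14, 7.17.2, 7.18, 14.0), significant follow-up findings are reported (7.17.2), and oral examinations are done at every scheduled follow-up. This stands. A reader might infer that an unrelated event leaves no trace at all; the documents do not support that. What can be lost is its status as an AE.

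A reader might also infer that the exemption biases the pain results, or that section 11 claims reduced pain as established. Neither holds. Pain is measured by questionnaire outside the AE route, and section 11 lists only potential benefits.

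It can be said that the exemption concerns reactions, while perforation and instrument separation are procedural complications; that 10.8 itself calls its items adverse events; and that nothing ties 10.8 to the word expected in 10.3. This is fair, and the documents do not support saying that primary safety events *are* excluded. They leave that reading open.

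Serious events have their own rule in 10.6, so it would be too strong to say that SAEs are excluded. Two instructions conflict, and because 10.2 defines an SAE as a kind of AE, the conflict should be settled in words.

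Finally, the 10.3 scope sentence may be meant as a body-region limit, not a causal test. Even so, it falls short of 10.1 and 10.6, and leaves doubt over reactions to medications, materials or chemicals that 10.8 lists as risks.

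**Conclusion.** The contradiction is in the current text and should be resolved. Section 10.3 conflicts directly with 10.1 and 10.6 and with its own list, and narrows the lower grades of 10.5. Investigator attribution can decide whether an event is recorded as an AE, with the greatest exposure for non-pain events between the procedure and month 6. Two of the five primary safety events appear on the anticipated-risk list and two more are defined partly by signs that can be exempted, with no override stated.

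The number of events affected cannot be computed from the documents. Any under-recording would lower the reported AE rate, but its size is unknown, and the safety analysis in 13.6 is a descriptive summary with no prespecified comparison. The conclusion assumes that sites apply 10.3 as written and that the investigator applies the relatedness filter.

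**What to change.** Reconcile 10.1, 10.3, 10.5, 10.6 and 10.8 in one amendment:

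- Delete the sentence limiting collection to AEs related to dental and endodontic procedures. Alternatively, restate it as a body-region scope that does not depend on cause and never applies to SAEs, and say in 10.1 that collection is narrower than the definition.
- State that events are recorded first and graded for causality afterwards under 10.5.
- Replace the exemption for expected reactions with a yes/no field on the AE CRF for whether the event is expected with root canal therapy, so that expected events can be tabulated separately. A severity cut-off is not a substitute, since 10.1 counts mild events.
- State that all SAEs and the five primary safety events are always recorded as AEs, whatever their expectedness or presumed cause.

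The cost is amendment wording, one CRF field, more AE forms and a higher reported AE rate. The analysis in 13.6 need not change.

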## **10.4** Unresolved Adverse Events

Any subject terminated from the study due to an AE will be followed until the outcome of the event is determined.

Any subject that is discontinued, withdrawn, or lost to follow-up will have this information documented on the End of Study CRF. This is considered the End of Study for the patient and all unresolved AEs must be marked as ongoing on the AE or AE Resolution CRF.

All other AEs will be followed through to the end of the study. Any unresolved AE at the subject's final visit must be marked as ongoing on the AE CRF.

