## 7.10 Inability to Complete Treatment

If, for any reason, Sonendo GentleWave treatment cannot be completed over the course of no more than two visits, the subject will be considered as a Treatment Incomplete Subject. Subjects in the Treatment Incomplete Cohort will be documented as such but will not be followed for the study. No additional data will be collected on the Treatment Incomplete Cohort. Reasons for incomplete treatment may include, but are not limited to, periodontal issues, uncontrolled bleeding, root fracture, patient reported pain, etc.

These subjects will be counseled by the PI on any treatment they require. Subjects in the Treatment Incomplete Cohort will be responsible for any standard of care treatment.

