# 10.6 Serious Adverse Event Reporting

PIs must report all Serious Adverse Events (SAEs) to the Sponsor within a timely manner of observing or learning of the event. For initial SAE reports, Investigators should record all case details that can be gathered within a timely manner on the SAE CRF and fax this information immediately upon completion to the Sponsor. The fax number is [contact].

Each SAE must be followed with appropriate medical management until it's resolved or assessed as chronic or stable regardless of whether or not, in the opinion of the Investigator, the event is

thought to be related to the procedure. The Investigator will be required to provide complete information concerning each SAE to the sponsor within in a timely manner. This information must be recorded in the subject's medical record and then transcribed onto the Adverse Event CRF. The completed Serious Adverse Event Report (SAE) (including the Investigator's opinion of the relationship of the SAE to the procedure/device under investigation), copies of related results/reports, consultant report(s), and other relevant information will be faxed and/or mailed to the Sponsor.

All SAEs as described above, covering the period from a subject's enrollment in the study through seven (7) days following a subject's completion as per protocol or premature discontinuation from the trial will be managed and reported. The decision to report potential SAEs beyond the seven (7) day post-study period will be at the discretion of the Sponsor, unless otherwise advised by the IRB.

In addition, Investigators must report all SAEs to their Institutional Review Board (IRB) and regulatory bodies according to applicable guidelines and regulations. A copy of the notification must also be submitted to the Sponsor.

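### Sections 10.4 and 7.10 conflict with 10.6 on serious adverse events that are open, or arise, when a subject leaves the study

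*Combined protocol and SAP*

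**What the plan says.** Section 10.4 sorts open adverse events by how the subject leaves. For one group it requires follow-up to outcome: "Any subject terminated from the study due to an AE will be followed until the outcome of the event is determined". For a second group it sets a closing status: "Any subject that is discontinued, withdrawn, or lost to follow-up will have this information documented on the End of Study CRF", and then "This is considered the End of Study for the patient and all unresolved AEs must be marked as ongoing". A last paragraph covers all remaining AEs. These are followed to the end of the study and marked ongoing if unresolved at the final visit. The section does not mention SAEs.

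Section 7.10 deals with subjects whose device treatment cannot be completed within two visits. They are recorded as Treatment Incomplete and not followed, and "No additional data will be collected on the Treatment Incomplete Cohort". The example reasons include root fracture, uncontrolled bleeding and patient-reported pain.

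Section 10.6 is the SAE section. It requires that "Each SAE must be followed with appropriate medical management until it's resolved or assessed as chronic or stable", whether or not the event is thought to be related to the procedure. Its reporting period starts at enrollment, and SAEs "through seven (7) days following a subject's completion as per protocol or premature discontinuation from the trial will be managed and reported". Reporting beyond that is left to the sponsor's discretion unless the IRB advises otherwise.

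**The concern.** An SAE that is open when a subject withdraws is subject to two instructions. One closes the record as ongoing; the other requires follow-up to an end state. For a Treatment Incomplete subject the tension is sharper, because 7.10 stops data collection altogether and not only the status of one form.

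The outcome and duration of serious events are at stake, and for Treatment Incomplete subjects so is whether later events are captured at all. Section 10.3 asks for duration, outcome and a narrative for each AE, which an early closure leaves incomplete. Sections 13.2 and 13.6 summarise safety for everyone who receives the procedure, so a stop in data on subjects whose treatment was abandoned falls within the population that the safety summary describes.

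**Working it through.** No figure in the plan is in dispute, so the check is a comparison of the passages.

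1. **Rules by exit status, for an event that is serious**

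| Exit status | 10.4 | 7.10 | 10.6 |
|---|---|---|---|
| Terminated because of an AE | Followed to outcome | Silent | Followed to an end state: consistent |
| Withdrawn, discontinued or lost | Marked ongoing at End of Study, no SAE exception | Silent | Followed to an end state: conflict if 10.4 is read literally |
| Treatment Incomplete | Not named; the general paragraph applies | No further data | Followed to an end state: conflict if 7.10 is read literally |

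2. **Are Treatment Incomplete subjects inside the 10.6 period?** Yes. Section 7.6 places enrollment at the start of LuxaBite or Tooth Cap placement, which 7.7 also makes the start of device treatment. A subject whose device treatment begins and is not completed is therefore enrolled, and the 10.6 period has begun. The documents do not say whether Treatment Incomplete counts as premature discontinuation, so the end of the reporting window is undefined for this group.

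3. **Do the sections refer to each other?** No. Section 10.6 also sends SAE information to the Adverse Event CRF, one of the forms that 10.4 tells the site to mark ongoing.

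4. **Which events are reached?** The window in 10.6 applies to SAEs only. Under 10.2, root fracture, bleeding or pain is serious only if it meets one of the listed criteria. For a non-serious root fracture the conflict is between the data stop in 7.10 and the all-treated safety summary in 13.6. A fracture that causes treatment to stop should already be recorded, because 10.3 covers AEs at treatment visits. Its outcome, and any event that appears later, are what could be missed.

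5. **Events not yet serious at exit.** One criterion in 10.2 is persistent or significant disability, and persistence can be known only through follow-up. An event closed as ongoing could later meet that criterion without anyone recording it.

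6. **How many subjects?** Section 13.1 allows 20% of 108 for lost to follow-up and Treatment Incomplete together: 0.20 × 108 = 21.6, which agrees with 108 − 86 = 22. This is a pooled attrition allowance. It is not split by exit status, it does not count subjects with an open event, and the documents give no SAE rate. The number affected cannot be derived.

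**The case against.** The strongest reply is that 10.6 is the specific rule for SAEs and already prevails. It has no stop at exit, it names premature discontinuation, and it uses a separate SAE form and report. Section 10.4 sets a CRF status and nowhere cancels 10.6, so a site could mark an event ongoing and still follow it. In addition, 9.7 to 9.9 class treatment-related exits that endanger the subject as terminations and reserve withdrawal and discontinuation for non-treatment-related reasons. Section 9.10 already requires three contact attempts for lost subjects. The primary safety endpoint is an incidence, which an ongoing flag does not alter.

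Much of this stands, and it rules out several stronger readings that a reader might infer:

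- **That outcomes of serious harm are lost.** The text supports only that they may be missing if 10.4 or 7.10 is applied literally.
- **That follow-up ends on the day of exit.** Section 10.4 refers to End of Study and names no day.
- **That Treatment Incomplete subjects fall in no class under 10.4.** Its last paragraph is a catch-all. What it delivers is unclear, however, because 7.10 says these subjects are not followed.
- **That 10.6 gives every AE at least 7 days.** It covers SAEs only.
- **That about 22 subjects are affected.** That figure is the attrition allowance.

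The reply does not dispose of 7.10. Termination under 9.7 is at the investigator's discretion, whereas Treatment Incomplete status follows whenever treatment cannot be completed, for any reason. The data stop in 7.10 can affect incidence as well as outcome. Voluntary withdrawal also remains open to a subject with an unresolved SAE.

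**Conclusion.** The conflict is real and the passages must be reconciled. Sections 10.4 and 7.10, taken at their word, do not provide for the SAE follow-up that 10.6 requires. The consequence is conditional: outcomes of SAEs open at exit may be absent from the database, and for Treatment Incomplete subjects later SAEs or primary safety events may be absent as well. The documents do not allow this to be sized, and the number could be very small.

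Two assumptions matter. First, the Safety Population in 13.2 is taken to include subjects who received only part of the device treatment. Second, the effect on the incidence of primary safety events rests on 13.6, which uses the Safety Population; the synopsis and 3.2 confine that endpoint to the Treatment Complete cohort. If the narrower definition applied, the gap would concern general safety reporting and not the primary safety endpoint. The effectiveness analysis is unaffected either way. A subject who cannot be reached, or who refuses contact, cannot be followed under any wording.

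**What to change.** Amend three points:

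1. In 10.4, state that 10.6 governs SAEs for every exit status, including Treatment Incomplete, and that an ongoing entry on the CRF does not end SAE follow-up. The same sentence would cover the final-visit wording in its last paragraph.
2. In 7.10, add the same cross-reference and limit the data stop to effectiveness data, so that SAEs and primary safety events are still captured for the Safety Population. Say how the 10.6 reporting window is counted for these subjects.
3. Name the telephone, mail and dentist contact in 7.19, which already lists adverse events, as the route for obtaining outcomes, subject to the subject's consent.

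This concerns data capture and reporting and changes no treatment rule. The cost is amendment wording and a few extra contacts or record requests through a procedure the protocol already has.
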